7.2 Criteria for exclusion of subjects

Patients who meet ANY of the following criteria will be excluded from the study:

1. Patients with confirmed hepatitis B virus co-infection (HBsAg positivity).
2. Patients with chronic HCV infection of genotypes other than 1
3. CD4 lymphocyte count <100 cells/mm³.
4. HIV RNA in plasma greater than 50 copies/mL
5. Platelet count less than 80,000/mm³

6. Patients who had to discontinue prior interferon or ribavirin therapy due to a serious adverse event that the investigator considered possible or probably related to ribavirin or interferon.
7. Treatment with ribavirin in the previous 90 days and with any interferon alfa in the month prior to the screening visit.
8. Hepatitis C treatment with any investigational product. Previous treatments with phytotherapy products with known hepatotoxicity are grounds for exclusion.
9. Participation in another clinical trial within 30 days prior to randomization or intention to participate in another clinical trial during participation in the present study.
10. History of hemoglobinopathy (e.g., thalassemia) or other cause of hemolysis, or hemolytic tendency.
11. Signs of decompensated liver disease, such as a history or presence of clinical ascites, hemorrhagic varicose veins, or hepatic encephalopathy.
12. Diabetic or hypertensive patients with signs of clinical importance on ophthalmological examination.
13. Pre-existing, unstable, or untreated psychiatric illness.
14. Any known pre-existing medical conditions that could interfere with the patient's participation in the trial and its completion.
15. Any current signs of alcoholism or other drug use.
16. Patients receiving opioid agonist substitution therapy but not participating in any opioid substitution maintenance program.

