4.3 Treatment Regimen

PEG-IFN alfa-2a or 2b and ribavirin will be provided by each hospital and will be administered in accordance with the approved technical data sheets.

BOC (Boceprevir). Provided by the study sponsor.

Description:

BOC is supplied in 200 mg capsules. Each capsule contains 200 mg of BOC, sodium lauryl sulfate, microcrystalline cellulose, lactose monohydrate, croscarmellose sodium, pregelatinized starch, and magnesium stearate packaged in number 0 hard gelatin capsules. Each capsule contains approximately 56 mg of lactose monohydrate. In people with lactase deficiency, the clinical manifestations of lactose intolerance require 3 to 5 g of lactose (4 to 7 times the total amount of BOC capsules) to appear.

Route of administration: oral

Dosage: total daily 2400 mg, (12 capsules).

Storage: keep in the fridge at a temperature between 2°C and 8°C. The products of the study must be stored in a safe place with limited access and in the storage conditions specified on the supply label.

[figure not shown]
Dosage Schedule:

Boceprevir is administered three times a day using a dosing schedule of 4 capsules every 8 hours. Actual times of dose administration may be modified to fit the patient's schedule, although 7- to 9-hour

intervals between administrations should be maintained. All doses of boceprevir will be given with food (a small snack is sufficient).

Study period and treatment:

All patients will receive an initial 4 weeks of bitherapy with Peg-Interferon and ribavirin (PR).
-If there is a decrease in HCV RNA greater than 1 logarithm with respect to baseline HCV-RNA, the patient will be included in the treatment scheme detailed below.

-If the RNA drop is ≤ 1 log at week 4, PR/boceprevir will be administered for an additional 44 weeks. All cirrhotic patients will receive PR for 4 weeks, followed by RP/boceprevir for another 44 weeks

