10.3 Evaluation of toxicity parameters

The classification system for drug toxicity is set out in the DAIDS Table for Grading the Intensity of Adverse Events in Adults and Children, which can be found on the DAIDS RSC website: <http://rsc.techres.com/safetyandpharmacovigilance/>.

Treatment of PEG-IFN Side Effects

Side effects of PEG-IFN usually include flu-like symptoms such as myalgia, arthralgias, headache, chills, low-grade fever, nausea, vomiting, and tiredness, as well as erythema, pain, and edema at the injection site. Less common are side effects of the central nervous system (CNS), such as depression, insomnia, anxiety, and irritability. Abnormalities of thyroid function have been described, as well as neutropenia, thrombocytopenia, and alopecia. The decrease in neutrophil and platelet count is usually dose-dependent and usually reaches nadir by week 4. Reductions in the total number of white blood cells may also occur, although usually not below normal levels. In week 2, dose-related decreases have been observed for other analytical parameters, such as albumin, globulin, total proteins, potassium and calcium; however, most parameters normalize by week 4 of treatment. Inflammation at the injection site occurs intermittently throughout treatment, but usually does not limit it. In general, all these effects are reversed by decreasing or interrupting the dose; patients cannot continue to take RBV and BOC if PEG-IFN is permanently discontinued.

Treatment of IFN-associated neutropenia

Patients who develop neutropenia during treatment may receive G-CSF (not provided by the study) at the discretion of the center investigator.

Table 1. Treatment of toxicity: neutropenia

Parameter	Downward dose adjustment of PEG-IFN
RAN (cells/mm ³)	
Grade 1 (1,000- 1,300)	None

Grade 2 (750999)	No dose adjustment is necessary; G-CSF at the discretion of the centre's researcher
Grade 3 (500749)	Immediately reduce the dose by UN* one level and administer G-CSF at the discretion of the center investigator. If neutropenia disappears, the dose may be increased at the discretion of the center investigator.

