- Dose delay of 3 to 5 days: Giving subsequent doses every 5 to 6 days until the patient gets back to their original schedule (for example, if Monday is the usual day of administration and the dose is delayed until Saturday, the next dose will be given on Thursday, the next dose on Tuesday, and the next dose on Monday).
- 6-day dose delay: discontinue that week's dose and continue with the usual schedule the following week (e.g. if Monday is the usual day of administration but the dose is delayed until the following Sunday, the dose is considered to have been interrupted and the next injection will coincide with the following week's dose, on Monday).
- Dose delay of 7 or more days: The investigator may resume administration of the study drug at any time up to 28 days after the last dose and, if necessary, administer the dose every 5 or 6 days until the weekly dose is received on the patient's usual scheduled day.

Treating the Side Effects of RBV

The most common AA in RBV treatment is anemia, which may be due to hemolysis or decreased release of red blood cells from the bone marrow. Anemia usually appears 1 to 2 weeks after you start receiving RBV and usually goes away within 4 to 8 weeks of withdrawal or reduction of the drug's dose. In patients with anemia secondary to RBV-induced hemolysis, an elevation of indirect bilirubin is common. BOC may increase the incidence or severity of anemia. In case of anaemia during treatment with BOC and RBV, the dose adjustment of RBV, as described below, takes precedence over BOC.

NOTE: A serious side effect of RBV is its teratogenicity; therefore, it is recommended not to administer RBV to pregnant or breastfeeding women and to men whose partner is pregnant. Women who become pregnant during the study will be required to discontinue study treatment and undergo withdrawal assessments.

The dose of RBV in this study will depend on weight at study entry (see section 5). The following table shows the recommendations for dose reduction in case of anemia. The administration of epoetin (EPO) will be at the discretion of the centre's researcher. If the administration of RBV is temporarily or permanently stopped, patients may continue to receive PEG-IFN and BOC.

Board. Recommended RBV dose reduction in anaemia

	Starting dose	Measure
--	---------------	---------

Hemoglobin <10 g/dL, ≥8.0 g/dL.	1,400 mg/day 1,200 mg/day	Decrease RBV to 1,000 mg/day
	1,000 mg/day	Decrease RBV to 800 mg/day

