The safety profile represented by nearly 1,500 patients treated with the combination of boceprevir with peginterferon alfa-2b and ribavirin is derived from pooled safety data from two clinical trials in treatment-naïve patients and one clinical trial in treatment-failed patients.

The most frequently reported adverse events in the BOC/PEG/RVB groups were largely the reflection of events that are associated with the treatment spine (PEG/RBV).

The most frequent adverse reactions were fatigue, anemia, nausea, headache and dysgeusia. Only two adverse events, anaemia and dysgeusia, are 20% more common in boceprevir-containing treatments and will be discussed as events of particular interest.

Boceprevir monotherapy did not cause a decrease in hemoglobin in either the animal studies or a phase I monotherapy study. In healthy adult males who received boceprevir for up to 57 days, no effects on red blood cell formation, survival, and destruction or on markers of anaemia were detected. However, boceprevir added to PEG and RVB therapy results in a gradual decrease in hemoglobin of approximately 1 g/dL.

Treatment of anemia in patients receiving boceprevir polytherapy is identical to that of anemia in patients treated with peginterferon plus ribavirin. The incidence of discontinuation of treatment due to anemia is just as low, close to 1%, both in the control group with PEGIFN plus RBV and in the experimental groups treated with boceprevir.

Anemia in patients treated with boceprevir is transient, as baseline hemoglobin values recover after treatment.

Based on the above data, BOC is usually well tolerated and has an AA profile similar to that of the standard of care (PEG-IFN + RBV) with the exception of dysgeusia, which is more common in patients treated with BOC. The anemia appears to be mainly due to exposure to RBV.

Rules for processing

The dose of BOC cannot be reduced in the study.

Anaemia should be treated initially by reducing the dose of ribavirin and an erythropoiesis stimulant whenever available and appropriate. For dysgeusia, attempts will be made to reduce symptoms (e.g., pills, plastic cutlery, etc.). Treatment of headache and nausea should also be symptomatic. **Grade 1 and 2 AEs require close follow-up but no change in treatment.**

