Prior to the start of treatment, a clinical examination, electrocardiogram and blood and urine sample will be taken (*SEE TABLE OF DAILY DETERMINATIONS*).

The data will be collected through an online electronic CRD.

15. Financing and Insurance

The promoter has taken out civil liability insurance in accordance with current regulations.

16. Publication Policy

The Promoter undertakes to publish the results, both positive and negative, of this study as stated in art. 39 of RD 223/2004.

17. Table of examinations and treatment during follow-up

Treatment Visit Schedule														
Clinical Evaluations	Day 1	ST 2a	ST 4	ST 6	ST 8	ST 10	ST 12	ST 16	ST 20	ST 24	ST 30	ST 36	ST 42	ST 48/dFT
Inclusion and exclusion criteria	X													
Vital signs	X	X	X	X	X	X	X	X	X	X	X	X	X	X
Weight	X									X				X
Physical examination	X		X				X			X		X		X
Adverse events	X	X	X	X	X	X	X	X	X	X	X	X	X	X
Concomitant medications	X	X	X	X	X	X	X	X	X	X	X	X	X	X
Confirmation of the use of contraceptive methods by the patient and his or her partner	X	X	X	X	X	X	X	X	X	X	X	X	X	X
Simplified Compliance Questionnaire	X	X	X		X		X		X	X		X	X	X
Haematology	X	X	X	X	X	X	X	X	X	X	X	X	X	X
TP/TTP	X						X			X				X
Blood biochemistry (simplified, fasting)		X	X		X		X		X		X		X	
Blood biochemistry (complete, not fasting)	X			X				X		X		X		X
Thyrotropin (TSH)	X						X			X		X		X
Serum pregnancy test (women only)	X													X
Urine pregnancy test (women only)		X	X	X	X	X	X	X	X	X	X	X	X	X
Samples for pharmacogenetics	X													
HCV RNA CPR*	X		X		X		X			X				X

All laboratory specimens should be obtained prior to administration of the first dose of study medication.

- Samples will be obtained for a genotypic resistance test if the patient has >100 IU/mL at week 12 or later. A single blood sample will be obtained for genetic studies.

Complete blood biochemistry: ALT, AST, creatinine, alkaline phosphatase, gammaglutamyl transferase (GGT), total bilirubin (direct and indirect), total proteins, albumin, uric acid, urea nitrogen, glucose, HbA1C (patients diagnosed with diabetes, either receiving pharmacological treatment or controlled with diet), amylase, lipase, sodium, potassium, chloride, phosphorus, calcium, triglycerides, and cholesterol.

Simplified blood biochemistry: alanine aminotransferase (ALT), aspartate aminotransferase (AST), creatinine, alkaline phosphatase, total bilirubin (direct and indirect), urea nitrogen, total proteins, albumin, uric acid and glucose.

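### Section 7.2 sets a platelet floor but no haemoglobin or neutrophil floor, so patients can start the lead-in at counts where 10.3 would cut the dose on treatment

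*Combined protocol and SAP*

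**What the plan says.** Exclusion 5 in section 7.2 rules out "Platelet count less than 80,000/mm³". Apart from the CD4 limit of 100/mm³, this is the only blood-count limit in 7.1 or 7.2. Exclusion 10 concerns haemoglobin disorders and haemolysis by diagnosis, without a value. Exclusion 14 lets the investigator exclude for a known condition that could interfere with taking part, also without a value.

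Under section 4.3 every patient first receives 4 weeks of peginterferon and ribavirin without boceprevir, and these two drugs "will be administered in accordance with the approved technical data sheets" (Annex I).

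Section 10.3 gives on-treatment dose rules for platelets, haemoglobin and neutrophils. On timing it says: "The decrease in neutrophil and platelet count is usually dose-dependent and usually reaches nadir by week 4". On ribavirin it says: "Anemia usually appears 1 to 2 weeks after you start receiving RBV". Section 10.1 confines the dose-adjustment rules to toxicity attributable to the study drugs.

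**The concern.** All three counts are expected to fall under the lead-in drugs and all three drive dose changes in 10.3, yet only one has an entry limit. A patient with haemoglobin 9 g/dL or neutrophils 700/mm³ meets no numeric exclusion. That patient is already past the first action value when the expected early falls begin.

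At stake is an avoidable early cytopenia and a dose reduction or interruption in a few patients, during the phase whose week-4 HCV RNA fall helps set treatment duration (section 8.1). Safety is also part of the primary objective, and section 11.3 reports grade 3 or higher events with a 95% confidence interval. A neutrophil count of 700/mm³ at entry already lies in the grade 3 band of Table 1 in 10.3, which would make later events in that patient harder to attribute.

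**Working it through.** The plan states no figure to reproduce here, and the sample size is not an input. The check sets the entry limits beside the dose rules.

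| Count | Entry floor (7.1, 7.2) | First dose action (10.3) | Interruption or stop (10.3) |
|---|---|---|---|
| Platelets | 80,000/mm³ | <50,000/mm³: peginterferon reduced | <25,000/mm³: peginterferon stopped for good (Table 2); whole combination stopped (Pegasys table) |
| Haemoglobin | none | <10 g/dL: ribavirin reduced | <8.0 g/dL (ribavirin table) or <8.5 g/dL (Pegasys table): ribavirin stopped |
| Neutrophils | none | <750/mm³: peginterferon reduced | <500/mm³: peginterferon deferred or suspended |

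**Margin = entry value − action value.**

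- Platelets at the floor: 80,000 − 50,000 = 30,000/mm³, and 30,000/80,000 = 37.5%. Between 50,000 and 99,999/mm³ Table 2 asks for no action, so a patient admitted at the floor starts inside a no-action band.
- Haemoglobin: with no floor, no margin is guaranteed. Example value, chosen for illustration: 9.0 g/dL is 10 − 9.0 = 1.0 g/dL below the first action value. It leaves 9.0 − 8.0 = 1.0 g/dL to stopping ribavirin, or 9.0 − 8.5 = 0.5 g/dL under the Pegasys table.
- Neutrophils: again no guaranteed margin. Example value: 700/mm³ is 750 − 700 = 50/mm³ below the first action value. It leaves 700 − 500 = 200/mm³ to interruption, and 200/700 = 28.6%.

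**Timing.** Ribavirin anaemia is expected from weeks 1 to 2 and the neutrophil low point by week 4, so both fall in the lead-in. Section 10.3 adds that "boceprevir added to PEG and RVB therapy results in a gradual decrease in hemoglobin of approximately 1 g/dL". That further fall can begin only after week 4, once counts at treatment weeks 2 and 4 are available, so it is not the early risk.

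**What cannot be computed.** The documents give no baseline distribution of haemoglobin or neutrophils and no g/dL figure for ribavirin's own effect in the lead-in. Neither the number of patients starting below these values nor the chance of crossing the next limit can be derived.

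**The case against.** The case for leaving 7.2 as it stands has real weight.

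- **The data sheets may already settle it.** Peginterferon and ribavirin are given under their data sheets, and section 8.2 points to the same annex for contraindicated treatments. Annex I is not available for this review, so starting values may already bind. This stands as a limit on the point. But 4.3 refers to the sheets for administration, and 7.1 and 7.2 do not cite them for eligibility.
- **Platelets differ in kind.** Only for platelets does 10.3 prescribe a definitive stop, after which ribavirin and boceprevir cannot continue either. Low neutrophils lead to deferral and resumption with optional G-CSF. Low haemoglobin leads to a recommended ribavirin reduction or a temporary stop, with EPO support. The protocol does not give this as its reason, but it makes a platelet-only floor understandable.
- **The population is already selected.** Inclusion 1 requires at least 12 weeks of earlier peginterferon/ribavirin. Exclusion 6 removes those who stopped it for a related serious event, exclusion 7 requires a washout, and exclusions 10 and 11 remove haemolytic causes and decompensated liver disease. These narrow the exposed group without setting a value.
- **Monitoring is close.** Haematology is scheduled at all 14 treatment visits, and earlier trials reported stopping for anaemia in about 1%. After the first dose, monitoring detects a problem but does not prevent a low start. The 1% counts discontinuations, not dose reductions, in trials whose entry limits are not given.

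A reader might infer that the protocol contradicts itself, admitting patients whose dose it must cut on Day 1. It does not: because 10.1 limits the dose rules to drug-attributable toxicity, a pre-treatment value triggers nothing in 10.3. What remains is that neither section tells the investigator what to do with a low pre-treatment haemoglobin or neutrophil count.

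**Conclusion.** The point holds as a modest eligibility gap that is cheap to close. On their face, 7.1 and 7.2 admit patients at haemoglobin below 10 g/dL or neutrophils below 750/mm³, counts at which 10.3 would reduce a dose if they arose on treatment. Platelets have a guaranteed 30,000/mm³ before first action; the other two counts have none.

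This rests on reading the enumerated criteria alone. If the Annex I sheets set starting values that the centres apply, the change only makes an existing rule explicit. Confidence is medium for that reason, and the number affected is unknown.

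A reader might also infer that early dose cuts in these patients would lower the SVR estimate. The documents do not support that: they give neither a frequency nor a link from lead-in dose reduction to response. The sample size and significance level are untouched.

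**What to change.** Add two exclusions to 7.2: haemoglobin <10 g/dL and neutrophils <750/mm³, or the data-sheet starting values if these are higher. Include any stricter haemoglobin value for stable heart disease. The Pegasys table in 10.3 suspends ribavirin in such patients if haemoglobin is still below 12 g/dL after 4 weeks at a reduced dose, so a 10 g/dL floor does not fit them. Require the result to be read before the first dose, on the blood count used for the platelet criterion.

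These floors prevent entry at an action value but add no headroom: at 10.0 g/dL the margin is 10.0 − 10 = 0. The clinical team should decide whether a buffer is wanted.

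The cost is two lines of text and a few more screening failures. No new test is needed: the platelet criterion already requires a count, haematology is scheduled on Day 1 before dosing, and section 14 says "Prior to the start of treatment, a clinical examination, electrocardiogram and blood and urine sample will be taken". The screening table, as extracted, lists no haematology. If Day 1 provides the only count, the first dose may wait briefly for the result.

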7.3 Withdrawal criteria

Treatment with the study drug will be terminated **immediately** during the study for any of the following reasons:

- Patient with HCV RNA >100 IU/mL in ST12 or detectable HCV RNA in ST24.
- Suicide or homicide thoughts or attempts.
- Major depression, major depressive episode.
- Positive test result for non-prescription opioids, methamphetamines, or cocaine.
- Pregnancy during the study.
- Express wish of the patient
- Virological rebound, defined as:

Any patient who obtains an undetectable HCV RNA and subsequently presents an HCV RNA > 1,000 IU/ml.

Once virologic failure has been identified, genotypic resistance will be characterized by HCV RNA sequencing in suitable samples, such as those collected at the time of failure and during the follow-up period.

Treatment with the study drug **may** be terminated during the study for any of the following reasons:

- The medical investigator determines that a SAE is possibly or likely related to the study drug.
- Failure to administer, evaluate, or other study requirements.

8. Treatment of Subjects

8.1 Treatment branches

An open-label, single-arm, multicenter study to evaluate the safety and efficacy of a regimen with boceprevir in polytherapy with peginterferon alfa-2b 1.5 µg/kg or peginterferon alfa-2a 180 µg/kg once weekly subcutaneously (s.c.) and oral ribavirin in adult patients with controlled HIV coinfection in whom prior treatment of chronic hepatitis C with peginterferon and ribavirin has failed.

Since early response to peginterferon (PEG-IFN) and ribavirin (RVB) at week 4 is predictive of response to treatment, either SVR or null response (high negative predictive value: 96%), the duration of response-guided treatment with BOC will depend on the response in ST4, ST8, and ST12.

Patients who achieve a reduction in HCV RNA viral load greater than or equal to one logarithmic unit at week 4 (after the bitherapy phase) will then undergo triple therapy for 32 weeks. If HCV RNA is undetectable at week 8, they will end the tto after 32 weeks of triple therapy and will be followed for another 24 weeks. If HCV RNA is detectable at week 8, at the end of the 32 weeks of triple therapy, patients will receive dual therapy with pegylated interferon and ribavirin for an additional 12 weeks and then follow up for 24 weeks.

Patients who do not achieve a decrease in HCV RNA viral load greater than one logarithmic unit at week 4 after the initial phase of bitherapy (or those who have grade 4 fibrosis - cirrhosis) will receive triple therapy for 44 weeks and will be followed for an additional 24 weeks.

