4.1 Identification of the investigational medicinal product

Generic name: Boceprevir

Trade name: Victrelis®

Composition: boceprevir 200 mg.

Pharmaceutical form: hard gelatin capsules.

Generic name: Peginterferon (alpha-2b or alpha-2a)

Trade name: Pegintron® or Pegasys®

Composition: peginterferon alfa-2b 80-150mcg or peginterferon alfa-2a: 180 micrograms

Pharmaceutical form: solution for injection

Generic name: Ribavirin Trade name:

Ribavirin Teva®.

Composition: ribavirin: 200 mg

Dosage form: hard capsule

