6.4 Trial treatments

DRUG SUPPLY AND LABELLING

In this study, 2 drugs already on the market and authorized for use in HIV-HCV co-infected patients will be used; peginterferon and ribavirin; The study drug, boceprevir, will be provided by MSD throughout the study and distributed by the Coordinating Center. For clinical trials carried out in Spain, relabelling in Spanish is mandatory.

See section 4.3

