7.1 Criteria for inclusion of subjects

A patient must meet ALL of the criteria listed below in order to participate:

1. To participate in the study, patients must have been treated with peginterferon alfa-2a plus ribavirin or peginterferon alfa-2b plus ribavirin for a minimum of 12 weeks. If a patient has received more than one of these guidelines, the most recent one will be considered.
2. The patient must have a previously documented HCC caused by genotype 1 virus (subtype a or b). Patients with other genotypes or with mixed genotypes will not be able to participate. The HCV RNA result at the screening visit should confirm genotype 1 virus infection and be >10,000 IU/mL.
3. The patient must have a liver biopsy with HCC-compatible histology and no other etiology or evaluation with Fibroscan. In the event of:
 - a. **Absence of cirrhosis.** Biopsies or Fibroscan must have been done within 18 months prior to the screening visit.
 - b. **Cirrhosis** No specific time frame is required.
4. All patients with cirrhosis should have an ultrasound scan performed within 6 months prior to the screening visit.
5. Patients must be receiving stable antiretroviral therapy with a CD4 lymphocyte count greater than 100/mm³ and an undetectable HIV plasma viral load (< 50 copies/mL) for more than 6 months. Antiretroviral therapy should contain raltegravir (at least for the past 6 weeks).
6. The patient must be 18 years of age or older.
7. HIV treatment should not contain EFV, NVP, ddI, d4T, AZT, or HIV protease inhibitors.
8. The patient should weigh between 40 and 125 kg.
9. The patient and partner must commit to acceptable contraception from at least 2 weeks prior to Day 1 and until at least 6 months after the last dose of study drug. (negative pregnancy test in women of childbearing potential) (Postmenopause is defined as the absence of menstruation during the year prior to study entry.)
10. Patients must be willing to give written informed consent and, in the opinion of the investigator, be able to follow the protocol visit design.

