Grade 4 (<500)	Study weeks 1 and 2: defer or discontinue administration until grade 2 is reached, then resume administration with dose reduction of DOS* levels. Study weeks 3 to 48: defer or discontinue administration until grade 2 is reached, then resume administration with a dose reduction of ONE level. Administer G-CSF at the discretion of the centre's investigator. If neutropenia disappears, the dose may be increased at the discretion of the center investigator.

* The dose reduction levels of PEG-IFN are indicated in the label.

Treatment of IFN-associated thrombocytopenia

Table 2. Treatment of toxicity: decreased platelet count

Platelet count (cells/mm3)	MEASURE
Grade 2 (50,000-99,999)	No
Grade 3 (25,000-49,999)	Halving the dose of interferon
Grade 4 (<25,000)	Suspend the PEG-IFN definitively.

* The dose reduction levels of PEG-IFN are indicated in the label.

Dose reduction of PEG-IFN

Dose reductions should be uniform between participating centers and patients. For this purpose, the following reductions shall be used:

Table 3. Guidelines for Recommended Dose Reduction of PEG-IFN 1.5 µg/kg

		Reduction of one level (decrease to 1.0 µg/kg)			Two-level reduction (decrease to 0.5 µg/kg)		
		Volume			Volume		
Weight at Sit Up*		Pen Size	Injection (ml)	Dosage (µg)	Pen Size	Injection (ml)	Dosage (µg)
40 to 50 kg	88 to 110 lbs	Redipen 50	0,45	45	Redipen 50	0,30	30
>50 to 60 kg	>110 to 132 lbs	Redipen 80	0,35	56	Redipen 50	0,30	30
>60 to 65 kg	>132 to 143 lbs	Redipen 80	0,40	64	Redipen 50	0,35	35
>65 to 75 kg	>143 to 165 lbs	Redipen 80	0,45	72	Redipen 50	0,35	35
>75 to 80 kg	>165 to 176 lbs	Redipen 80	0,5	80	Redipen 50	0,40	40
>80 to 85 kg	>176 to 187 lbs	Redipen 120	0,35	84	Redipen 50	0,40	40

>85 to 95 kg	>187 to 209 lbs	Redipen 120	0,40	96	Redipen 50	0,50	50
>95 to 105 kg	>209 to 231 lbs	Redipen 150	0,35	105	Redipen 50	0,50	50
>105 to 125 kg	>231 to 275 lbs	Redipen 150	0,35	105	Redipen 50	0,50	50

* Use the usual rounding methods: values between 0.1 and 0.4 kg should be rounded down and those between 0.5 and 0.9 kg should be rounded up.

Missed or deferred doses of PEG-IFN

If a dose of PEG-IFN is delayed but is finally administered, the following guidelines are recommended for the following scheduled doses:

- Dose delay of 1 or 2 days: administer on the usual day of administration of the week (for example, if Monday is the usual day of administration and the dose is delayed to Wednesday, the next dose will be administered as usual, on Monday).

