	800 mg/day	Decrease RBV to 600 mg/day
	600 mg/day	Decrease RBV to 400 mg/day (Initiate treatment with EPO at the discretion of the center's investigator)
Hemoglobin <8.0 g/dl	All doses	Temporarily discontinue the RBV
Symptomatic decrease in haemoglobin will be treated at the discretion of the centre's investigator.		

Reintroduction of RBV

In the event that RBV is temporarily stopped due to anaemia, haemoglobin values should be checked again after two weeks and then at two-week intervals until stabilised. If hemoglobin returns to an acceptable level, RBV should be reintroduced at doses of 600 mg/day (with a regimen of 200 mg in the morning and 400 mg in the evening). The dose may be increased by 200 mg/day every two weeks until the initial dose is reached.

Treatment of anemia with EPO is recommended, but this is not provided in the study. On the other hand, it is not advisable to administer EPO with hemoglobin values ≥10 g/dl. If necessary, at the discretion of the centre investigator, the dose of RBV may be reduced by a haemoglobin value ≥10 g/dl.

Increasing the dose of RBV

Once haemoglobin has returned to an acceptable level, patients who have had their RBV dose reduced without discontinuing their administration may, at the discretion of the centre investigator, increase the dose by 200 mg/day every two weeks until the initial dose is reached.

Missed doses: If a patient misses a dose of RBV, they should take it as soon as possible, along with food, during the same day. If a full day has passed, you should skip the missed dose and continue with the normal schedule of administration. In no case should the dose be doubled to "compensate" for the missed dose.

Treatment of Adverse Events Related to PEG-IFN alfa-2a and Ribavirin (PEGASYS™ PCR)

Dose adjustment in case of adverse reaction

	Reduce ribavirin to 600 mg	Suspend ribavirin	Reduce Pegasys to 135/90/45 micrograms	Suspend Pegasys	Suspended r la combination
Absolute neutrophil count			<750/mm3	<500/mm3	
Platelet count			<50,000/mm3 >25,000/mm3		<25,000/mm3

Hemoglobin - absence of heart disease	<10 g/dl , and ≥ 8.5 g/dl	<8.5 g/dl			
Hemoglobin - stable heart disease	Decrease ≥ 2 g/dL for any 4 weeks	< 12 g/dL despite 4 weeks at a reduced dose			

Treating BOC Side Effects

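### Section 8.1 gives peginterferon alfa-2a per kilogram, which cannot be squared with the fixed microgram amounts in sections 4.1 and 10.3

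*Combined protocol and SAP*

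**What the plan says.** **Alfa-2a amount.** Section 8.1, under Treatment of Subjects, gives "peginterferon alfa-2a 180 µg/kg once weekly subcutaneously". Section 4.1 lists "peginterferon alfa-2a: 180 micrograms", with no per-kilogram unit. The alfa-2a adverse-reaction table in section 10.3 has a column headed "Reduce Pegasys to 135/90/45 micrograms", again with no per-kilogram unit. Section 7.1 sets the eligible weight: "The patient should weigh between 40 and 125 kg".

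**Related text.** Table 2 of section 10.3, on low platelets, is not limited to one peginterferon and prescribes "Halving the dose of interferon" at grade 3. The footnotes to Tables 1 and 2 add "The dose reduction levels of PEG-IFN are indicated in the label". Section 6.4 says "See section 4.3", and section 4.3 says that peginterferon and ribavirin "will be administered in accordance with the approved technical data sheets".

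**Ribavirin in anaemia.** Section 10.3 has two tables. The first is introduced for ribavirin in the study generally, is worded as recommendations, and sets the reduction by starting dose. The second is headed for alfa-2a with ribavirin, reduces to a single 600 mg level, and has a separate row for stable heart disease. For the ribavirin dose itself, section 10.3 refers to section 5, which contains only the objectives.

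**The concern.** Section 8.1 gives an amount, a frequency and a route for alfa-2a. A reader who takes it at face value has a weight-based amount, and the protocol's own reduction steps for the same product are fixed amounts that cannot be reached from it by any sensible reduction. This concerns the stated amount of a study treatment, so the passages have to agree. Section 10.3 also asks for peginterferon reductions to be uniform across centres and patients, which presupposes a starting amount that fits the steps.

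For ribavirin the stake is smaller. Two alfa-2a patients with the same haemoglobin could be handled differently depending on which table their site follows.

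**Working it through.** No derivation in the plan lies behind the 180 µg/kg figure, so the check is one of units and consistency.

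**1. Literal weekly amount under section 8.1** (180 µg/kg × weight, with the weight limits from section 7.1)
- At 40 kg: 180 × 40 = 7,200 µg
- At 125 kg: 180 × 125 = 22,500 µg

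**2. Against the 180 micrograms in section 4.1**
- 7,200 / 180 = 40 and 22,500 / 180 = 125, so 40 to 125 times as much

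**3. Against the largest step in section 10.3 (135 µg)**
- 7,200 / 135 = 53.3 and 22,500 / 135 = 166.7

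**4. The steps as a share of each possible starting amount**
- Of 180 µg: 135/180 = 75%, 90/180 = 50%, 45/180 = 25%
- Of the literal section 8.1 amount: at most 135/7,200 = 1.9%, at least 45/22,500 = 0.2%

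**5. Halving under Table 2.** Table 2 halves interferon at platelets of 25,000 to 49,999, the band in which the alfa-2a table lists the three steps.
- From the literal section 8.1 amount: 7,200/2 = 3,600 µg to 22,500/2 = 11,250 µg, which is 26.7 to 83.3 times 135 µg and none of the listed steps
- From 180 µg: 180/2 = 90 µg, a listed step

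Step 5 repeats the same mismatch and is not separate evidence. The comparisons show which passages agree with one another, not which is right.

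**6. The two ribavirin tables, for an alfa-2a patient without heart disease**

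| Haemoglobin (g/dL) | Starting dose (mg/day) | First table | Second table |
|---|---|---|---|
| 8.5 to <10 | 1,400 | 1,000 | 600 |
| 8.5 to <10 | 1,200 | 1,000 | 600 |
| 8.5 to <10 | 1,000 | 800 | 600 |
| 8.5 to <10 | 800 | 600 | 600 |
| 8.5 to <10 | 600 | 400 | no reduction |
| 8.0 to <8.5 | any listed | reduce | suspend |
| <8.0 | any listed | stop temporarily | suspend |

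In the 8.5 to <10 band the reduction targets differ for three of the five starting doses and agree for one (800 mg). For the fifth (600 mg) the first table reduces and the second does not. The resulting dose is therefore the same for only one of the five. The heart-disease row exists only in the second table; that is a gap in the first table and not in itself a contradiction.

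**The case against.** The strongest reply is that section 8.1 opens as a description of the study, and that the operative rule is section 4.3, which sends peginterferon and ribavirin to the approved data sheets; section 6.4 points there too. The per-kilogram unit follows directly after the weight-based alfa-2b dose and looks like a slip, and the text shows other traces of translation, so the sites' working version may not carry it. The 180 micrograms in section 4.1 is a composition line and not a dosing rule. A ratio against a reduced step is also larger than the like-for-like 40 to 125.

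Much of this stands as a limit on practical risk. The fixed steps in section 10.3 are the stronger evidence, and no actual exposure is shown. It does not remove the contradiction. No text says that the data sheets or the label override section 8.1. The sheets (Annex I) are not in the text available for review, so what they say could not be checked. If they differ from section 8.1, sections 4.3 and 8.1 give two instructions with no stated order; if they agree with it, section 10.3 still conflicts.

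On ribavirin, the alfa-2a heading may naturally be read as the more specific rule, the first table only recommends, and symptomatic falls in haemoglobin are left to the centre investigator. That is why the point ranks lower. Still, the only precedence sentence on anaemia sets ribavirin adjustment ahead of boceprevir and does not rank the two tables.

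**Conclusion.** The main point holds with high confidence as a matter of text, and it must be fixed. The alfa-2a amount in section 8.1 is incompatible with sections 4.1 and 10.3 at every eligible weight, by a factor of 40 to 125 against the former and 53 to 167 against the largest step in the latter. These factors rest on a literal reading of the unit and on the protocol's own weight limits. Whether the unit is a slip cannot be settled from the documents.

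The ribavirin overlap is real but lesser. Its practical reach cannot be sized, because the documents give neither the share of patients on alfa-2a nor, given the empty reference to section 5, their starting ribavirin doses. Neither point touches the sample size of 128 or the primary analysis of sustained virologic response.

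**What to change.** The sponsor should:

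- reconcile sections 4.1, 4.3, 8.1 and 10.3 on the alfa-2a unit, and state whether the data sheets cited in section 4.3 take precedence over section 8.1;
- as a lesser clarification, reconcile the two ribavirin anaemia tables in section 10.3 or state which patients each covers, including those with stable heart disease;
- correct the reference to section 5 for the ribavirin dose;
- notify sites of the corrected wording.

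Which dose or threshold is right is for the sponsor to settle. The cost is a wording correction and a notice to sites. The sample size, primary analysis and data collection do not change.
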